#### **2.1.5.5 *Vital signs variables***

Vital signs include heart rate (bpm), and systolic and diastolic blood pressure (mmHg) (see study flowchart in Section 1.3 of the protocol).

Body weight (kg) will be presented with the vital signs.

#### **2.1.5.6 *Electrocardiogram variables***

Not applicable

#### **2.1.6 *Efficacy endpoints***

Efficacy endpoints are tertiary/exploratory.

HbA1c and FPG are measured in a blinded fashion at a central laboratory, for scheduled (see study flowchart in Section 1.3 of the protocol) and unscheduled assessments.

In case of premature permanent IMP discontinuation, the process described in [Section 2.5.1](#) will be applied to retrieve efficacy assessments performed at the end of treatment visit (Visit 8000).

### ***Efficacy observation period***

- The randomized period for efficacy variables is defined as the time from randomization date up to Week 16 (Visit 7), regardless of study treatment discontinuation.

### ***Efficacy endpoints***

All efficacy endpoints will be derived on the randomized period using the intent-to-treat (ITT) population. All HbA1c/FPG values will be used, regardless of adherence to treatment.

The following efficacy endpoints will be calculated:

- Change from baseline to Week 16 in HbA1c (%), defined as the HbA1c value at Week 16 - HbA1c value at baseline.
- Change from baseline to Week 16 in FPG (in mg/dL and mmol/L), defined as the FPG value at Week 16 - FPG value at baseline.

#### **2.1.7 Pharmacodynamic/genomics endpoints**

Not applicable.

#### **2.1.8 Quality-of-life endpoints**

Not applicable.

#### **2.1.9 Health economic endpoints**

Not applicable.

## **2.2 DISPOSITION OF PATIENTS**

This section describes patient disposition for both patient study status and the patient analysis populations.

For patient study status, the total number of patients in each of the following categories will be presented in the clinical study report using a flowchart diagram or summary tables

- Screened patients, defined as all patients who signed the informed consent.
- Screen failure patients and reasons for screen failure.
- Randomized patients, as defined in [Section 2.3](#).
- Treated but not randomized patients.
- Randomized and not treated patients.

- Randomized and treated patients,
  - Completed patients: Patients who completed the **treatment period** (as reported on the EOT CRF page).
  - Patients who did not complete the **study treatment** as per protocol.
  - Patients who discontinued the **study treatment** by main reason (related to COVID-19 or not for reasons “Adverse event” and “Other”) for definitive treatment discontinuation.
  - Patient’s reason (related to COVID-19 or not for reasons “Adverse event” and “Other”) for permanent **treatment** discontinuation.
- Patients who completed the **study period** (as reported on the EOS CRF page).
  - Patients who discontinued the **study** by main reason (related to COVID-19 or not for reason “Other”) for premature study discontinuation.
- Status at last study contact

For all categories of patients (except for the screened and nonrandomized categories) percentages will be calculated using the number of randomized patients as the denominator.

Patients with the following deviations will be identified and described in separate listings:

- Treated but not randomized patients.
- Randomized and not treated patients.
- Randomized but not treated as randomized.

Kaplan-Meier (KM) plots/estimates of the cumulative incidence of IMP discontinuation due to any reason, or due to AE, will be provided. Time to treatment discontinuation will be defined as the number of days from the first dose of IMP until the day of treatment discontinuation. All completers will be considered as censored observations. The censoring time will be the number of days from the first dose of IMP until the last dosing date.

Lists of participants who prematurely discontinued treatment and/or study will be provided with reasons for discontinuation, including reasons related to COVID-19.

All critical or major protocol deviations (including randomization and drug-dispensing irregularities, see [Section 2.2.1](#)) will be summarized by treatment group among randomized patients (number and percentages). Critical or major protocol deviations will also be summarized according to COVID-19 impact.

Patients impacted by COVID-19 are defined as patients with major impact of COVID-19 on study conduct, including premature EOT/EOS due to COVID-19 and/or critical or major protocol deviations related to COVID-19. The number and percentage of patients impacted or not by COVID-19 will be presented, along with the type of impact, and a listing of participants impacted by COVID-19 will be provided.

A table of patient disposition by visit according to COVID-19 impact will also be provided, based on the eCRF comment page. Each impacted visit will be described according to the following categories:

- Visit not done,
- Visit partially done on site,
- Visit partially done by phone,
- Complete visit but delayed.

Additionally, the analysis populations for pharmacokinetic, immunogenicity, safety and efficacy will be summarized in a table by patient counts on the randomized population:

- PK population as defined in [Section 2.3.1](#),
- Anti-insulin aspart antibody population as defined in [Section 2.3.3](#),
- Safety population as defined in [Section 2.3.2](#),
- Efficacy population: ITT population as defined in [Section 2.3.4](#).

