### **7.1 DISCONTINUATION OF STUDY INTERVENTION**

#### **7.1.1 Definitive discontinuation**

The IMP should be continued whenever possible.

In case the IMP is stopped, it should be determined whether the stop can be made temporary; definitive IMP discontinuation should be a last resort. Any IMP discontinuation must be fully documented in the eCRF. In any case, the participant should remain in the study as long as possible.

Definitive intervention discontinuation is any intervention discontinuation associated with the definitive decision from the Investigator not to re-expose the participant to the IMP at any time during the study, or from the participant not to be re-exposed to the IMP whatever the reason.

The participants may withdraw from treatment with IMP if they decide to do so, at any time, and irrespective of the reason. Participants are encouraged to discuss their intent of stopping the IMP with the site before doing so in order for questions to be addressed, concomitant therapy to be adjusted if needed, and a follow-up assessment arranged. All efforts must be made to document the reasons for treatment discontinuation in the source documents and in the eCRF.

A participant should withdraw from treatment with IMP and NIMP in case of the following:

- Temporary discontinuation of the IMP of more than 10 days in total.
- Intercurrent conditions that require discontinuation of IMP/NIMP (eg, for laboratory abnormalities according to the decision tree in Appendix 5 [[Section 10.5](#)] as long as the abnormality persists and if the casual relationship of the concerned event and the IMP/NIMP is possible according to the Investigator's best medical judgment).
- If, in the Investigator's opinion, continuation with the administration of IMP/NIMP would be detrimental to the participant's well-being.
- Pregnancy (in female participants).
- Confirmed intolerance to the allocated dose of IMP/NIMP.
- At the participant's own request, ie, withdrawal of consent for treatment.

It is important to collect data for all participants, under treatment or not, during the whole duration of the study. A high rate of missing data could jeopardize interpretation of the study results. Refer to the SoA ([Section 1.3](#)) for data to be collected at the time of IMP discontinuation and follow-up and for any further evaluations that need to be completed.

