## 1.3 DETERMINATION OF SAMPLE SIZE

Approximately 184 participants are planned to be randomly assigned to either one of the following treatment groups: alternating use of SAR341402 and NovoLog or continuous use of NovoLog (in a 1:1 ratio), with a minimum of 146 evaluable participants (73 per treatment group) for the primary PK evaluation expected at the end of the study. If the number of study participants with evaluable PK data is determined to have been reached before all planned 184 participants are randomized, then the study randomization may be stopped sooner.

[figure not shown]
The sample size calculations were performed based on the expected variability of the primary PK endpoints AUClast, AUC, and Cmax following injection of a predefined, fixed dose of SAR341402 or NovoLog (ie, 0.15 U/kg) at Week 16.

A sample size of 146 evaluable participants (73 participants per arm) will ensure that the 90% CI for the estimated treatment ratio is within the acceptance range of [0.8 – 1.25] with at least 90% power; assuming a true ratio between 0.95 and 1.05 (switching arm / non-switching arm) and a total standard deviation on natural log scale of 0.35 or lower.

Sample size calculations were made using SAS® Software Version 9.4.

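### The SAP labels a Kaplan-Meier curve the cumulative incidence of IMP discontinuation due to AE without saying how non-AE stops are handled; if they are censored, the curve slightly overstates it

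*SAP*

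**What the plan says.** SAP section 2.2 plans two curves with one estimator: "Kaplan-Meier (KM) plots/estimates of the cumulative incidence of IMP discontinuation due to any reason, or due to AE, will be provided". The event time runs from first dose: "Time to treatment discontinuation will be defined as the number of days from the first dose of IMP until the day of treatment discontinuation". The censoring rule is short: "All completers will be considered as censored observations", and "The censoring time will be the number of days from the first dose of IMP until the last dosing date". Nothing is said about patients who stop for a non-AE reason when the curve is for AE, and the SAP names no competing-risk estimator.

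The same section tabulates treatment discontinuation by main reason, adverse event among them; apart from the screened and nonrandomized categories, "percentages will be calculated using the number of randomized patients as the denominator". It also plans listings with reasons. SAP section 2.4.5.2 adds counts and percentages of patients with TEAEs leading to permanent IMP discontinuation, with the safety population as denominator. Protocol Table 7 (section 9.4.3) requires an incidence table for these events too.

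Protocol section 7.1.1 describes a definitive discontinuation as a decision "not to re-expose the participant to the IMP at any time during the study". Its listed routes include some that need not be adverse events, such as pregnancy or the participant's "own request, ie, withdrawal of consent for treatment".

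**The concern.** For any-reason discontinuation every stop is an event, so Kaplan-Meier with completers censored is the right tool. The AE curve is different. A patient who has definitively stopped at their own request is no longer taking IMP and cannot later stop it because of an AE. Censoring that patient treats them as still able to have the event at the same rate as those who remain. One minus Kaplan-Meier then describes a hypothetical setting in which nobody stops for other reasons, which is not a cumulative incidence.

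Two things are at stake, both modest. The curve could show a higher figure than the planned percentage tables for the same patients, with no explanation in the plan. And because the rule for non-AE stops is unwritten, two programmers could produce different AE curves from the same data.

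**Working it through.** **Plan's own figure.** The documents state no rate, precision or power for discontinuation, so there is nothing to reproduce on this point. The plan's one power statement (at least 90% with 73 evaluable per arm) concerns the PK comparison. It reproduces at 90.3% for a true ratio of 0.95 and 91.0% for 1.05, and does not depend on these curves.

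**Inputs.**
- Arm size: SAP section 1.3 says "Approximately 184 participants are planned to be randomly assigned", in a 1:1 ratio, so 184/2 = 92 per arm.
- Total discontinuation T: assumed, 5% to 30%.
- Share of stops due to AE, s: assumed, 10%, 25% or 50%.
- The value T = 20.65% is 38/184, from (184 − 146)/184. It is used only as a convenient upper-range value.

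**Formulas, with constant hazards for both kinds of stop.**
- Total cumulative hazard: H = −ln(1 − T). The AE part is s × H.
- True cumulative incidence for AE (the Aalen-Johansen target): T × s.
- One minus Kaplan-Meier with non-AE stops censored: 1 − exp(−sH) = 1 − (1 − T)^s.

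Example: T = 10%, s = 25%. True value 0.10 × 0.25 = 2.50%. Kaplan-Meier gives 1 − 0.90^0.25 = 1 − 0.9740 = 2.60%.

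| T | s | True | 1 − KM | Excess (points) |
|---|---|---|---|---|
| 5% | 10% | 0.50% | 0.51% | 0.01 |
| 5% | 25% | 1.25% | 1.27% | 0.02 |
| 10% | 25% | 2.50% | 2.60% | 0.10 |
| 15% | 25% | 3.75% | 3.98% | 0.23 |
| 20.65% | 10% | 2.07% | 2.29% | 0.22 |
| 20.65% | 25% | 5.16% | 5.62% | 0.46 |
| 20.65% | 50% | 10.32% | 10.92% | 0.60 |
| 30% | 25% | 7.50% | 8.53% | 1.03 |
| 30% | 50% | 15.00% | 16.33% | 1.33 |

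For T from 5% to 20.65% the relative excess is about 1% to 11%. In an arm of 92, one participant is 1/92 = 1.09 points, so 0.60 points is 0.60/1.09 = about 0.55 of a participant.

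**Extreme ordering.** Suppose 19 of 92 stop and every non-AE stop precedes every AE stop.
- 5 AE, 14 other: true 5/92 = 5.43%; Kaplan-Meier 5/(92 − 14) = 5/78 = 6.41%; excess 0.98 points.
- 10 AE, 9 other: true 10/92 = 10.87%; Kaplan-Meier 10/83 = 12.05%; excess 1.18 points.

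**The other reading of the silent rule.** If non-AE stops were instead kept in the risk set to the end of treatment, the first case would give 5/92 = 5.43% in any order, and there would be no excess. The bias therefore depends on a rule that the SAP does not state.

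**Effect on the contrast between arms.** Hold the true AE figure at 3% in both arms.
- Other-cause stopping 10% (T = 13%, s = 3/13) gives 3.16%; 17.6% (T = 20.6%, s = 3/20.6) gives 3.30%. Gap 0.14 points.
- Other-cause stopping 5% (T = 8%) gives 3.08%; 20% (T = 23%) gives 3.35%. Gap 0.27 points.
- Standard error of a 3% proportion in 92: √(0.03 × 0.97/92) = 1.8 points; of the difference, 1.8 × √2 = about 2.5 points.

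**The case against.** The strongest reply is that the SAP contains no stated error. It leaves a rule unwritten, and one way of filling the gap gives the right answer. That stands: the overstatement follows from the customary censoring of non-AE stops, not from SAP text.

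Second, the quantity of interest is already planned as crude percentages in SAP sections 2.2 and 2.4.5.2. Treatment has a planned fixed length and only completers are named as censored, so those percentages are close to what a correct curve would reach at the end of treatment. This also stands, and it limits the point to a plotted curve and its estimates.

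Third, a reader might infer that in an open-label trial the AE curves of the two arms would visibly separate because other-cause stopping differs. The documents do not support that. They give no discontinuation rates or split by reason. Under the assumed imbalances the artificial gap is 0.14 to 0.27 points against a standard error of about 2.5.

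Fourth, a reader might take 38/184 as the plan's expected discontinuation. It is the allowance for participants without evaluable PK data. SAP section 2.3.1 shows that such participants are also lost through injection deviations on the profile day and through insufficient or uninterpretable data.

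None of these replies makes censored Kaplan-Meier an estimator of cumulative incidence for one cause among several.

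**Conclusion.** The point holds as a small correction to one descriptive display. With non-AE stops censored, the AE curve never falls below the cumulative incidence, and it exceeds it once any AE stop follows a non-AE stop. The likely size is a fraction of one participant per arm. About 1 point or slightly more needs an extreme ordering or total discontinuation near 30%. These sizes rest on assumed totals, assumed AE shares and, outside the extreme case, constant hazards.

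A reader should not go on to infer that the trial's conclusions are at risk. The curves carry no test or decision rule, the safety analyses are descriptive, and the PK comparison, sample size and type I error do not use them. The reason to act is that the label, the estimator and the planned tables should describe the same quantity.

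**What to change.** In SAP section 2.2, keep Kaplan-Meier for any-reason discontinuation and replace the AE part with a sentence such as: *For IMP discontinuation due to AE, the cumulative incidence will be estimated by the Aalen-Johansen method, with definitive discontinuation for any other main reason as the competing event and completers censored at the last dosing date.*

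The curve will then agree with the crude tables, apart from randomized but untreated patients in the table denominator and any late stops during the extended treatment that SAP section 1.4 allows because of COVID-19.

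The cost is one sentence and a standard option in PROC LIFETEST of SAS 9.4, the software named in SAP section 5. The reasons and dates are already collected, and no other analysis changes.

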### **2.2.1 Randomization and drug dispensing irregularities**

Randomization and drug-dispensing irregularities occur whenever:

1. A randomization is not in accordance with the protocol-defined randomization method, such as a) an ineligible patient is randomized, b) a patient is randomized based on an incorrect stratum, c) a patient is randomized twice, or d) in a dynamic randomization scheme the treatment assignment is, in fact, not random, due to a computer program error.

OR

2. A patient is dispensed an IMP kit not allocated by the protocol-defined randomization, such as a) a patient at any time in the study is dispensed a different treatment kit than as randomized (which may or may not contain the correct-as-randomized IMP), or b) a nonrandomized patient is treated with IMP reserved for randomized patients.

Randomization and drug-dispensing irregularities will be monitored throughout the study and reviewed on an ongoing basis.

The major or critical randomization and drug-dispensing irregularities will be documented in the clinical study report. If the number of irregularities is large enough to make a tabular summary useful, the irregularities will be categorized and summarized among randomized patients (number and percentages). Nonrandomized, treated patients will be described separately.

Randomization and drug-dispensing irregularities to be prospectively identified include but are not limited to:

- Kit dispensation without IRT transaction

- Erroneous kit dispensation
- Randomization by error
- Patient randomized twice
- Stratification error

## 2.3 ANALYSIS POPULATIONS

Patients who are dispensed study drug without calling the IRT at Visit V3 (treated but not randomized) or before calling the IRT are considered nonrandomized patients. They are excluded from any population for analysis, including safety. However, if these patients experienced any significant safety event, they will be documented separately in the clinical study report.

The randomized population consists of all screened patients who have a treatment kit number allocated and recorded in the IRT database, regardless of whether the treatment kit was used.

For any patient randomized more than once, only the data associated with the first randomization will be used in any analysis population. The safety experience associated with any later randomization will be assessed separately.

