### **6.3 MEASURES TO MINIMIZE BIAS: RANDOMIZATION AND BLINDING**

All participants will be centrally assigned to randomized study treatment using an IRT system.

Randomization will be stratified by HbA1c obtained at the Visit 1 (<8.0% versus ≥8.0%).  
Randomization ratio is 1:1.

A randomized participant is a screened participant who has a treatment kit number allocated and recorded in the IRT database, regardless of whether the treatment kit was used. A participant cannot be randomized more than once in the study.

The treatment kit number list is generated centrally by Sanofi. The IMPs and NIMPs for the treatment period are packaged in accordance with this list. Designated Sanofi personnel provide the treatment kit number list and the randomization scheme to the centralized treatment allocation system (IRT). Then, the IRT generates the participant randomization list according to which it allocates treatment arms to the participants.

The treatment kits for the treatment period, open-label boxes identified with treatment numbers, are allocated to the participants by the IRT using the treatment number of the boxes.

At Visit 1, the Investigator or designee contacts the IRT for allocation of the participant number. The participant identification (participant number) is composed of 12-digit number containing the 3-digit country code, the 4-digit center code and the 5-digit participant chronological number (which is 00001 for the first participant screened in a center, 00002 for the second participant screened in the same center etc.).

At Visit 3 (Day 1, Randomization), the Investigator or designee has to contact the IRT for the first treatment kit(s) allocation (randomization) by providing some information (such as participant number provided by IRT at Visit 1, etc.). Afterwards the IRT is contacted again each time a new treatment kit(s) allocation is necessary, ie, the visits as indicated in the SoA (see [Section 1.3](#)) or when additional IMP/NIMP supplies are needed.

Returned IMPs and NIMPs must not be re-dispensed to the participants.

SAR341402 in the SAR341402 SoloStar pen and the control drug, NovoLog in the NovoLog FlexPen are distinguishable. Therefore administration of SAR341402/NovoLog throughout the trial is to be open-label. Potential bias will be reduced by the following steps:

- The specific IMP to be taken by a participant will be assigned centrally using an IRT.

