**Table 4 - Populations for analyses**

Population	Description
Screened	All participants who sign the ICF
Randomized	All screened participants who have a treatment kit number allocated and recorded in the IRT database, regardless of whether the treatment kit was used
Evaluable for PK (PK)	All participants without deviation that could significantly impact the PK analysis (eg, missing or incorrect SC injection on PK profile day) and for whom PK data are considered sufficient and interpretable
Intent to Treat (ITT)	All randomized participants, irrespective of compliance with the study protocol and procedures, analyzed in the treatment group to which they are randomized
Per Protocol (PP)	Subset of the ITT population, which includes all randomized and exposed participants, who do not definitively discontinue IMP allocated by randomization during the 16-week period, who perform Week 16 visit and who do not present major or critical protocol deviations that could significantly impact the analysis
Safety	All randomized participants who receive at least one dose of IMP (regardless of the amount of IMP administered). Participants will be analyzed according to the intervention they actually received.
Immunogenicity (AIA)	All participants from the safety population with at least one AIA sample available for analysis (ie, collected during the on-treatment period and at least 8 hours after the last administration of meal-time insulin). Participants will be analyzed according to the intervention they actually received.

AIA: anti insulin aspart antibody; ICF: informed consent form; IMP: investigational medicinal product; IRT: interactive response technology; ITT: intent to treat; PK: pharmacokinetic; PP: per protocol; SC: subcutaneous

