### 2.3.2 Safety population

The safety population is defined as all randomized patients who receive at least one dose of IMP, analyzed according to the treatment actually received.

In addition:

- If a patient is dispensed IMP and is lost to follow-up without any documented evidence whether or not the patient took IMP, the patient will be considered exposed and included in the safety population.
- Randomized patients for whom it is unclear whether they took the study medication will be included in the safety population as randomized.
- Non randomized but treated patients will not be part of the safety population, but their safety data will be presented separately.

- Randomized patients having taken at least one kit of SAR341402 will be considered in the switching arm. Patients randomized in the switching arm but having taken only Novolog as treatment will be considered in the non-switching arm.

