### **2.3.4 Efficacy population**

#### **2.3.4.1 *Intent-to-treat population***

The efficacy population will be the ITT population, which includes all randomized patients, irrespective of compliance with the study protocol and procedures.

Patients will be analyzed for efficacy analyses in the treatment group to which they are randomized.

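### SAP 2.3 drops from every population participants given drug before the IRT call, even when the IRT then records their assignment, contrary to the protocol and its own next paragraph

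*SAP*

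**What the plan says.** The opening paragraph of SAP 2.3 covers two groups: participants dispensed drug at Visit 3 with no IRT call, and participants dispensed drug ahead of the call. Of both it says: "or before calling the IRT are considered nonrandomized patients. They are excluded from any population for analysis, including safety". It adds that any significant safety event in these people will be documented separately in the study report.

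The next paragraph of the same section defines randomisation by the IRT record alone: "The randomized population consists of all screened patients who have a treatment kit number allocated and recorded in the IRT database", whether or not the kit was used. Protocol 6.3 says the same: "A randomized participant is a screened participant who has a treatment kit number allocated and recorded in the IRT database, regardless of whether" the kit was used. Neither definition depends on when drug was handed over.

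The populations follow from that definition:

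- ITT, Protocol Table 4: "All randomized participants, irrespective of compliance with the study protocol and procedures, analyzed in the treatment group to which they are randomized". SAP 2.3.4.1 agrees: "which includes all randomized patients, irrespective of compliance with the study protocol and procedures".
- Safety, Protocol Table 4: "All randomized participants who receive at least one dose of IMP (regardless of the amount of IMP administered"). SAP 2.3.2 likewise starts from randomised participants with at least one dose. It adds: "Non randomized but treated patients will not be part of the safety population, but their safety data will be presented separately".

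SAP 2.2.1 lists dispensing errors, including a kit other than the one allocated, as irregularities to be monitored and documented. It attaches no exclusion to them.

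**The concern.** Handing out drug before the call is a site procedural error. It does not undo an assignment that the IRT goes on to make and record. Both documents say that ITT membership survives procedural non-compliance, yet the first paragraph of SAP 2.3 withdraws it for this one error, along with membership of Safety and everything built on it.

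A programmer facing such a participant has one paragraph that puts the person in the randomised population and another that takes the person out. If the exclusion is applied, someone with a recorded arm, up to 16 weeks of exposure and possibly a Week 16 PK profile leaves the primary PK analysis and the by-arm hypoglycaemia, adverse event and antibody tables. The analysis sets would then differ from those in Protocol Table 4.

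**Working it through.** **1. The definitions side by side.**

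| Situation at Visit 3 | Kit recorded in IRT? | Protocol 6.3, Table 4; SAP 2.3 second paragraph | SAP 2.3 first paragraph | Conflict |
|---|---|---|---|---|
| Drug given, IRT never called | No | Not randomised | Nonrandomised, excluded | None |
| Drug given, IRT called afterwards, kit recorded | Yes | Randomised | Nonrandomised, excluded | Yes |
| IRT called, then drug given | Yes | Randomised | Not addressed | None |

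Only the middle row is at fault, and only because of the second limb of the exclusion.

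**2. Following the middle row through the populations.**

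- ITT: in, because compliance with procedures is irrelevant.
- Safety: in, if at least one dose was taken.
- AIA (SAP 2.3.3): drawn from Safety, so in if an eligible sample exists.
- PK (SAP 2.3.1): starts from randomised participants and removes only those with deviations that could significantly affect the PK analysis or with inadequate PK data. Early dispensing at Visit 3 has no evident bearing on a profile taken at Week 16.

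The first paragraph of SAP 2.3 reverses all four.

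**3. Could the early kit be the right product?** Both arms take NovoLog in weeks 0 to 4 (Protocol 1.1; SAP 1.4). A NovoLog kit handed over just before the call would therefore hold the product that either arm assigns. A SAR341402 kit would not. The documents do not say which kit such a participant would have received.

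**4. Power.** Inputs, from Protocol 9.1 and 9.2: 90% CI within 0.80 to 1.25 (two one-sided tests, each at 0.05), log-scale SD 0.35, true ratio 0.95 to 1.05, 73 evaluable per arm, about 184 randomised.

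Reproducing the plan at ratio 0.95:

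- SE = 0.35 × √(2/73) = 0.0579.
- Distance to the nearer limit = ln 0.95 − ln 0.80 = −0.0513 + 0.2231 = 0.1719.
- Normal approximation: n per arm = 2 × 0.35² × (1.645 + 1.282)² / 0.1719², which rounds up to 72.
- Exact power, integrating over the variance estimate with 144 degrees of freedom: 90.34% at ratio 0.95, 91.0% at 1.05, 97.1% at 1.00.
- Smallest n per arm reaching 90% exactly: 73 at 0.95 and 71 at 1.05.

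The stated 73 per arm (146) is reproduced.

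The number dispensed drug early is not given; I assume 0 to 10. If every loss came off an arm already at exactly 73, with the other arm held at 73 and ratio 0.95:

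| Lost from one arm | Power |
|---|---|
| 0 | 90.3% |
| 1 | 90.2% |
| 2 | 90.0% (89.97%) |
| 5 | 89.4% |
| 10 | 88.2% |

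Losing one from each arm (72 and 72) gives 89.98%.

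The condition in that sentence matters: 146 counts evaluable participants, and the plan randomises 184 − 146 = 38 more (38/184 = 20.7%). Losses come out of that surplus first.

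**The case against.** The best case for leaving the text alone is that it covers a rare event and costs nothing measurable. Several parts of that case stand, and they limit what a reader may infer.

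- **Bias.** It is tempting to call this a post-randomisation exclusion that biases the comparison. The trigger occurs before any arm is assigned, so the assignment cannot influence it. The rule departs from the ITT definition, but no between-arm bias is shown.
- **Power.** It is tempting to say that losing one participant per arm breaks the 90% claim. That holds only if the whole surplus of 38 has gone. Protocol 9.2 allows early stopping of randomisation, but only once the evaluable number is reached.
- **Safety data.** Reading SAP 2.3 alone, one might conclude that only significant events would be reported. SAP 2.3.2 promises separate presentation of the safety data without that limit, and the common rules in SAP 2.4.5 list data from people outside the safety population. The data leave the by-arm tables; they are not lost.
- **Correct treatment.** One might say that the rule discards correctly treated participants. It can, if the early kit was NovoLog, but the documents do not say so. A kit handed over before the call was not IRT-allocated at that moment, which is itself an irregularity.
- **Undeclared change.** SAP 1.5 and 1.6 do not list the rule, but they cover major changes, and Protocol 9.4 leaves the description of populations to the SAP. The omission is not an error in itself.

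One could also argue that the clause was meant only for people who never reach allocation. The first limb already covers them, so on that reading the second limb adds nothing, and the text does not say it.

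None of this removes the contradiction between the two paragraphs of SAP 2.3.

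**Conclusion.** The point holds as an inconsistency in one clause. For participants dispensed drug early and then recorded in the IRT, SAP 2.3 gives a result contrary to its own definition of randomised and to the protocol's ITT and Safety sets.

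Its practical size is small. The number affected is unknown, probably very small and possibly zero, and no effect on bias or on the stated power has been demonstrated. The conclusion rests on the text and on one assumption: that the situation can arise, with a call following early dispensing and the IRT recording a kit. The SAP's separate mention of dispensing before the call indicates that its authors thought it could.

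**What to change.** In SAP 2.3, limit the exclusion to participants never recorded as randomised in the IRT. State that those dispensed drug before the call but then recorded in the IRT stay in the randomised and ITT populations, in Safety if dosed, and in the PK and AIA populations if they meet those criteria. Report the early dispensing as an irregularity under SAP 2.2.1.

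The cost is about one sentence and no new data; the sample size is unchanged. There are two small consequences to write down:

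- SAP 2.3.2 places anyone who took a kit of SAR341402 in the switching arm, and SAP 2.3.3 also analyses by treatment received. A participant whose early kit was SAR341402 and who was then assigned to the non-switching arm would therefore be analysed in the switching arm for Safety and AIA, while staying as randomised in ITT.
- The schedule of activities requires baseline evaluations before randomisation. If an early dose was taken before them, the affected baseline values should be flagged.
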